7.1.2.9.7 Duration of Response

Duration of overall response: The duration of overall response is measured from the time that measurement criteria are met for CR or PR (whichever is first recorded) until the first date that recurrent or progressive disease is objectively documented (taking as reference for progressive disease the smallest measurements recorded since the treatment started). The duration of overall CR is measured from the time measurement criteria are first met for CR until the first date that recurrent disease is objectively documented. Please note that objective documentation implies confirmation of response by imaging.

Duration of stable disease: Stable disease is measured from the start of the treatment until the criteria for progression are met, taking as reference the smallest measurements recorded since the treatment started. The duration of stable disease is determined by the interval at which images are obtained (initially at weeks 6 and 12, and then every 12 weeks thereafter).

7.1.2.9.8 Progression-Free Survival (PFS)

PFS is defined as the time from initiation of study drug until the first documented, confirmed progression of clinically evaluable brain metastases based on mRECIST criteria, systemic disease based on RECIST criteria, or death. If there is progression of disease that is then confirmed on a follow up scan at least 4 weeks later, the initial date of documented progression should be used in the PFS analysis.

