4.2.3 Rationale for Endpoints

4.2.3.1 Efficacy Endpoints

Primary endpoint:

Best brain metastasis response rate (BMRR), defined as PR and CR per modified RECIST 1.1.

Secondary endpoints:

Best overall objective response rate, defined as PR and CR per RECIST 1.1.

PFS, defined as the time from start of study drug administration to the date of the first documentation of disease progression or death from any cause, whichever occurs first.

OS, defined as the time from start of study drug administration to date of death from any cause.

Duration of brain metastasis response, defined as the time from response to the time of the first documentation of intracranial disease progression.

Safety and rate of adverse events, particularly neurologic adverse effects, which include worsening of edema and development of radiation necrosis.

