7.1.2.9.2 Tumor Imaging During the Study

The first on-study imaging assessment for best BMRR by brain MRI should be performed at 6 weeks (42 days ± 7 days) from the date first study dose. Response assessment will be confirmed at 12 weeks. Subsequent tumor imaging should be performed every 12 weeks (84 days ± 7 days) or more frequently if clinically indicated. Imaging timing should follow calendar days and should not be adjusted for delays in cycle starts. Imaging should continue to be performed until disease progression is identified by the Investigator.

Best overall objective response should be confirmed by repeat imaging assessment. Initial best overall response assessment will be done by CT scans (preferred) performed at 6 weeks (42 days \pm 7 days) from the date first study dose. Response assessment will be confirmed at 12 weeks. Subsequent tumor imaging should be performed every 12 weeks (84 days \pm 7 days) or more frequently if clinically indicated. Imaging timing should follow calendar days and should not be adjusted for delays in cycle starts.

Participants who have disease progression may continue on treatment at the discretion of the Investigator and study PI provided they have met the conditions detailed in Sections 5.5.4.

In participants who discontinue study treatment, tumor imaging should be performed at the time of treatment discontinuation (\pm 4 week window). If previous imaging was obtained within 4 weeks prior to the date of discontinuation, then imaging at treatment discontinuation is not mandatory.

In participants who discontinue study treatment without documented disease progression, every effort should be made to continue monitoring their disease status by tumor imaging using the same imaging schedule used while on treatment (every 12 weeks) to monitor disease status until the start of a new anticancer treatment, disease progression, pregnancy, death, withdrawal of consent, or the end of the study, whichever occurs first.

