8.3 Statistical Analysis Plan

This section outlines the statistical analysis strategy and procedures for the study. If after the study has begun, changes are made to primary and/or key secondary hypotheses, or the statistical methods related to those hypotheses, then the protocol will be amended (consistent with ICH Guideline E9).

All baseline patient demographics and clinical characteristics will be summarized by mean/standard deviations and count/frequency for continuous and categorical variables respectively. All analyses will be completed as intent to treat.

Intracranial and Objective Response Rate

The primary endpoint is the best brain metastasis response rate of pembrolizumab in combination with lenvatinib. For the primary objective, the proportion of patients that experienced an intracranial response in each cohort will be estimated with corresponding 95% confidence interval.

The combination will be deemed worthy of further study as outlined in the Simon 2-stage designs in Section 8.2.

For objective response rate, the proportion of patients experience an objective response in each cohort will be estimated with corresponding 95% confidence interval.

PFS and OS

The non-parametric Kaplan-Meier method will be used to estimate median survival, along with survival at 1 year and 2 years.

Participants without documented event at the time of analysis will be censored at the date of last clinical evaluation for each outcome.

Duration of Intracranial Response Analysis

Duration of intracranial response will be evaluated by the Kaplan-Meier method. Intracranial responses will be analyzed separately from extracranial responses. If the patient has SD/PR/CR in the brain but PD in the body, then the patient will still be considered to have an ongoing intracranial response.

Statistical Methods for Safety Analyses

AEs will be coded using the standard Medical Dictionary for Regulatory Activities (MedDRA) and grouped system organ class. AEs will be graded by the investigator according to the NCI CTCAE, v5.0.

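### PFS has two incompatible definitions that Section 8.3 does not reconcile, and intracranial duration of response gives death no role; where this matters, both medians run long

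*Combined protocol and SAP*

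**What the plan says.** All references are to the combined protocol and SAP.

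- **PFS, Section 4.2.3.1:** "PFS, defined as the time from start of study drug administration to the date of the first documentation of disease progression or death". All causes of death count. Confirmation is not mentioned.
- **PFS, Section 7.1.2.9.8:** "PFS is defined as the time from initiation of study drug until the first documented, confirmed progression of clinically evaluable brain metastases", or of systemic disease by RECIST, or death. If progression is "confirmed on a follow up scan at least 4 weeks later, the initial date of documented progression should be used in the PFS analysis".
- **PFS and OS analysis, Section 8.3:** Kaplan-Meier, with this censoring rule: "Participants without documented event at the time of analysis will be censored at the date of last clinical evaluation for each outcome". The section does not say which PFS definition applies, and it has no rule for progression that is never confirmed or for new anticancer therapy.
- **Imaging in the initial course, Section 7.1.2.9.2:** "Imaging should continue to be performed until disease progression is identified by the Investigator". A repeat scan to confirm progression, 4 to 12 weeks later, is written only for the second course (7.1.2.9.3).
- **Follow-up, Section 7.1.5.3.3:** confirmed progression or new anticancer therapy moves the patient to telephone contact every 12 weeks.
- **Duration of intracranial response, Section 4.2.3.1:** "Duration of brain metastasis response, defined as the time from response to the time of the first documentation of intracranial disease progression". Section 8.3 analyses it by Kaplan-Meier. If the body progresses while the brain does not, "then the patient will still be considered to have an ongoing intracranial response". Death is not mentioned in either place.

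**The concern.** The two PFS definitions can give different event counts from the same patients. With neither chosen in Section 8.3, the choice could be made after the data are seen.

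Under the 7.1.2.9.8 version, a patient with one progression scan who then changes treatment may never have the second scan. That progression would not count on its own date. For duration of intracranial response, a responder who dies of extracranial disease has no event under the stated definition and would enter the Kaplan-Meier analysis as censored. Section 8.2 itself foresees deaths from extracranial disease in the melanoma cohort, though before the first response evaluation.

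The control is historical (Section 1.0). The stated hypotheses are that the combination improves PFS and OS and prolongs intracranial response (Section 3.2). Medians that run long would favour those hypotheses.

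**Working it through.** The plan states no target median, event count or power for PFS or duration of response, so there is no planned figure to reproduce.

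**1. Can the schedule confirm progression?** Scans fall at weeks 6 and 12, then every 12 weeks, each within ±7 days (7.1.2.9.2). The gaps are 6, 12 and 12 weeks. With the earlier scan a week late and the later one a week early, they are 6-2 = 4, 12-2 = 10 and 12-2 = 10 weeks. Every next scheduled scan therefore meets the 4-week requirement. Confirmation fails only if that scan is not done or cannot be compared. The documents leave these routes open:
- Imaging may end at the first progression (7.1.2.9.2).
- The end-of-treatment scan is waived if the last one was within 4 weeks (6.1, 7.1.2.9.2).
- New therapy leads to telephone follow-up (7.1.5.3.3).
- Local treatment of more than 25% of target lesions counts as progression, but the treated lesion is then no longer evaluable (5.5.4).

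**2. Direction for PFS.** An unconfirmed progression can be handled in two ways under 7.1.2.9.8.
- Censored at or after the progression scan: an event becomes a censoring, and the Kaplan-Meier curve is nowhere lower.
- Followed to death: the event time is the same or later for every patient, so the median being estimated cannot be shorter. In a single small data set the estimate can still move a little either way because of censoring in between.

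A confirmed progression is dated back to the first scan and is not affected.

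**3. Size for PFS (illustration).** The share of progressions never confirmed is not in the documents; 10%, 25% and 50% are assumed, unrelated to prognosis. The simulation used 200,000 patients per run, the scan schedule above, exponential times and administrative censoring between 24 and 60 months. Assumed medians in months for time to progression, death without progression and survival after progression:
- RCC-like: 13, 80, 12
- Melanoma-like: 8.5, 60, 9
- Short: 4, 40, 8

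The first two were set near the median PFS of 11.7 months (RCC, 4.2.1) and 7.6 months (melanoma, 4.2.2) quoted for this combination.

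| Scenario | Unconfirmed share | Median PFS, 4.2.3.1 | 7.1.2.9.8, censored at scan | 7.1.2.9.8, followed to death |
|---|---|---|---|---|
| RCC-like | 10% | 12.0 | 13.8 | 13.8 |
| RCC-like | 25% | 12.0 | 15.5 | 14.4 |
| RCC-like | 50% | 11.8 | 19.3 | 18.3 |
| Melanoma-like | 10% | 8.3 | 8.3 | 8.3 |
| Melanoma-like | 25% | 8.3 | 11.0 | 11.0 |
| Melanoma-like | 50% | 8.3 | 13.8 | 12.9 |
| Short | 10% or 25% | 5.5 | 5.5 | 5.5 |
| Short | 50% | 5.5 | 8.3 | 8.1 |

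The change runs from none to 13.8/8.3 = 1.66 times. It can be zero at low shares because detected progressions fall on the scan grid.

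**4. Size for duration of intracranial response.** Let λP be the hazard of intracranial progression, λD the hazard of death without it, and q = λD/(λP+λD). With constant hazards:
- median with deaths censored = ln 2/λP
- median with death counted = ln 2/(λP+λD)
- ratio = (λP+λD)/λP = 1/(1-q)

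| q (assumed) | 10% | 20% | 30% | 50% |
|---|---|---|---|---|
| Ratio | 1.11 | 1.25 | 1.43 | 2.0 |

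For scale only, take 9.9 months (the RCC median duration of response in 4.2.1) as the median with death counted. The death-censored median would be 9.9/0.9 = 11.0, 9.9/0.8 = 12.4, 9.9/0.7 = 14.1 or 9.9/0.5 = 19.8 months.

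**5. Reach.** The decision rules in Section 8.2 use only response counts (4 or more of 27; 7 or more of 29). Neither uses PFS or duration.

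**The case against.** A reader might infer that the plan counts only confirmed progression, that its schedule often cannot confirm it, and that real events are therefore routinely censored. The documents do not support that reading.

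- Section 4.2.3.1 requires no confirmation, and the Section 8.3 censoring sentence is at least as compatible with it as with 7.1.2.9.8.
- The scan gaps permit confirmation. Section 5.6 ties discontinuation to confirmed radiographic progression and allows treatment beyond progression, so some patients will be rescanned. The flow chart also appears to mark imaging in survival follow-up.
- Death is an event in both PFS definitions and survival is checked every 12 weeks, so an unconfirmed progression followed by a known death may be a late event rather than a censoring.

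All of this stands, but it does not guarantee a second scan. Sections 2.1 and 5.3 stop treatment at progression without asking for confirmation.

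On duration of response, analysing the brain separately from the body is a deliberate and coherent choice. The censoring sentence is printed under PFS and OS, so censoring at death is inferred from the stated end event and the Kaplan-Meier method. Under the independent constant hazards used above, the ratio compares two different quantities; it does not demonstrate informative censoring. That too stands, and it is why the statement here is relative to a definition that counts death.

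A reader might also extend the point to OS. There the direction is opposite: counting deaths learned by telephone while censoring living patients at an earlier clinic date would shorten OS. The phrase about each outcome may also mean an outcome-specific last evaluation.

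**Conclusion.** The point holds in limited form. PFS is defined in two incompatible ways, Section 8.3 does not choose, and no rule covers progression that is never confirmed. If 7.1.2.9.8 is applied, median PFS is the same or longer than under 4.2.3.1. Duration of intracranial response has no rule for death, and as written its Kaplan-Meier median runs long relative to a definition that counts death.

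The size cannot be derived from the documents. Over the assumed ranges it is 0 to about 66% for median PFS and 11% to 100% for median duration. Those figures rest on assumed shares of unconfirmed progressions and deaths, and on constant hazards.

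Both endpoints are secondary and descriptive, with no test or numerical benchmark planned. The primary endpoint and the Simon decisions are untouched. The wording should be settled before analysis, but the trial's main conclusion does not depend on it.

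**What to change.** - **PFS:** use the 4.2.3.1 definition in 7.1.2.9.8 and 8.3: first documented progression (mRECIST in the brain or RECIST in the body) or death from any cause, without confirmation. Confirmed-progression PFS can be kept as a sensitivity analysis if wanted.
- **Censoring:** censor PFS at the last adequate tumor assessment, and OS at the last date known alive, including telephone contact.
- **Duration of intracranial response:** define it from first response to intracranial progression or death, censored at the last brain MRI. Alternatively, report the cumulative incidence of intracranial progression with death as a competing event. Body progression alone may still leave the response ongoing.

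The cost is a change of wording in the definitions and the SAP, with no new data. The medians may be shorter, and the main PFS analysis may count some progressions that a later scan would not have confirmed.

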7.1.2.10 Tumor Tissue Collection and Correlative Studies

7.1.2.10.1 Collection and Shipment of Specimen(s):

Before initiation of systemic therapy, surgical specimens of brain tumor or extracranial tumor will be obtained (either archival or as a new biopsy). Archival tissue must have been formalin fixed and embedded in paraffin. If fresh tissue from a new biopsy site is obtained, tissue will be prioritized for formalin fixation and embedding in paraffin, but effort will be made to flash freeze a portion of tissue in liquid nitrogen, and SNAP frozen tissue will be stored for further studies. Please see the Procedures Manual for tissue requirements and handling of tissue.

7.1.2.10.2 Site(s) Performing Correlative Study:

The stored tissue specimens will be analyzed at Yale University. Please see Section 8.3 on Statistical Analysis for information on how results will be analyzed.

7.1.2.10.3 Correlative Studies

Correlative studies will be conducted on the pre-treatment tissue specimen. A number of additional biomarkers will be studied for their potential predictive value in pre-treatment CNS specimens taken at the time of surgery or LITT and/or on tumor tissue from a systemic site. These exploratory studies include (but are not limited to):

- 1) Markers to be studied on tumor cells: B7H1, PDL2, B7H4, Galactin-9.
- 2) Percent of tumor sample that constitutes CD4 and CD8 cells
- 3) Markers on T cells: LAG-3 on CD4 cells, PD1-H (PD-1 homologue) on T cells, CTLA4 on T cells TIM3 on T cells

Patients who undergo surgical procedures (either of the CNS or peripheral) while on systemic treatment will also be asked to provide a research specimen to determine changes in the above markers in the context of response or resistance to therapy.

Levels of all of the above markers will be measured by a method of Automated Quantitative Analysis (AQUA) of in situ protein levels in [name] laboratory at Yale University. This method has been validated for epithelial cancers and melanoma and has shown to be more precise than pathologist-based scoring of 3,3'-diaminobenzidine stain. AQUA is highly reproducible and quantitative, as reviewed (Jilaveanu et al., 2009). Tumors will be stained with a number of fluorophores: A tumor mask for melanoma will be made using a cocktail of anti-S100 and anti-Melan-A. The methods for masking tumor have been described in the literature (Berger et al., 2004; Camp, Chung, & Rimm, 2002; Kluger et al., 2008). The mask will be conjugated to Cy-3, and will be differentiated from the target antigen, which will be conjugated to Cy-5. After fluorescent staining is completed, images are taken at the different wavelengths, and the images will be analyzed using algorithms that have been extensively described 58. A monochromatic, high-resolution images of each histospot will be obtained using the 10 \times objective of an Olympus AX-51 epifluorescence microscope (Olympus) with automated microscope stage and digital image acquisition driven by a custom program and macrobased interfaces with IPLabs software (Scanalytics, Inc.). Tumor will be distinguished from stromal elements by the tumor mask signal. The signal intensity of the target biomarker will be scored on a scale of 0-255 (the AQUA score). This will provide quantitative results.

Biomarker analysis will be conducted using standard methods. Associations between continuous AQUA scores and binarized outcome variables (such as response) will be done by ANOVA. Cox univariate analysis will be used to study the associations between the survival endpoints and biomarker expression; Kaplan Meier curves will be generated to depict the association between binarized biomarker levels and survival endpoints. Multivariable models will be generated to predict response.

Immune monitoring will be performed as a part of this study. Peripheral blood lymphocytes (PBLs) and plasma (approximately 40cc) will be collected before cycles 1, 2, and 3, and subsequent to that, before every 3rd cycle thereafter, until patients come off of study. PBMCs will be separated and cryopreserved for T and B cell studies. Samples will be stored for immunophenotyping studies and serological profiling to be done using the Yale Cy-TOF core facility, or flow cytometry and by Eve Technologies.

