3.3 Exploratory Objective

- (1) Objective: To identify predictive biomarkers to pembrolizumab and lenvatinib which correlate with intracranial and extracranial responses and toxicity via a combination of immunohistochemical, transcriptional, protein, and genetic assays using pre-treatment tumor and pre- and on-treatment blood samples.

Hypothesis: Analysis of patient samples will identify useful biomarkers to help determine, at baseline, patients who will respond or who will experience toxicity from combination pembrolizumab and lenvatinib.

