7.1.2.9.4 Modified RECIST 1.1 Assessment of CNS Disease

Modified RECIST 1.1 will be used as the primary measure for assessment of intracranial tumor response, date of intracranial disease progression, and as a basis for all protocol guidelines related

to intracranial disease status (eg, discontinuation of study treatment). Up to 5 intracranial, previously untreated target lesion in the brain will be followed for response and progression. Size is considered the tumor's largest diameter. Measurements from multiple lesions are summed to calculate the sum of the diameters (SD). The SD calculated on a baseline scan performed within 28 days of study drug initiation will be used as a reference to determine the objective response of the clinically evaluable lesions. All responses must be confirmed at 12 weeks with an equivalent or better response. Please refer to the original RECIST criteria if further reference is necessary. Please see section 7.1.2.9 for response assessment in patients requiring local therapy while on study.

Measurable disease

Specification of a minimal lesion diameter for measurable lesions reduces the potential for variation in the measurement of smaller lesions due to slice selection and volume averaging. The minimal lesion diameter should be greater than or equal to 2 times the section thickness and a minimum of 5mm. A previously irradiated lesion will not be measured as a target lesion unless it is documented to have progressed since treatment.

Non-measurable disease

Non-measurable lesions at baseline are important in clinical trials because tumor progression may occur at these sites. Non-measurable lesions include enhancing lesions that are less than the specified smallest measurable diameter (5mm when slice thickness is 2.5mm or twice the slice thickness), hemorrhagic or predominantly cystic or necrotic lesions that are difficult to accurately measure and track, and lesions that are indeterminate for metastatic disease. Intrinsic T1- hyperintensity is noted within hemorrhagic lesions that may be misinterpreted as enhancing tumor, and for this reason, the precontrast T1-weighted image must be examined at baseline to prevent this error. Non-measurable lesions should be briefly described on the imaging case report form for each study {Henson, 2008 #303}.

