All subjects will be included in the safety analysis. Incidence tables will be generated to summarize incidence of patients reporting at least one episode of each specific adverse event, incidence of adverse events causing withdrawals and incidence of serious adverse events. Listing of adverse events by patients will include the time to onset, the duration of each event, the severity of each event, and the relationship of the event to study therapy, whether it was a serious event, and whether it caused withdrawal.

Exploratory Objectives

Biomarker Studies

Immunohistochemical evaluation of baseline tumor PD-L1 staining, TIL populations, and other immune and angiogenic factors that may predict tumor sensitivity to this drug combination will be compared between non-responders (SD and PD) versus responders (PR and CR) using a mixed methods approach, that adjusts for repeated measures over time and response as defined above. If there are differences by time, pairwise contrasts will be utilized to assess for specific differences at various time points, adjusting for multiple comparisons using the Tukey method.

For patients who have on-treatment tumor samples, comparison will be made to pre-treatment tissue for PD-L1 staining, TIL populations, and other immune and angiogenic factors that may predict tumor sensitivity. Differences in these markers by response will be assessed using two-sample t-test.

Blood samples collected before and on treatment will be analyzed for cytokines and by flow cytometry. Data will be analyzed by a repeated measures ANOVA and adjusted for multiple comparisons via Tukey method.

TIL will be extracted from resected pre-treatment specimens and subjected to immunophenotyping studies to characterize T and B cells using single-cell RNA-sequencing. Data will be analyzed by a repeated measures ANOVA and adjusted for multiple comparisons via Tukey method.

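### Tissue-marker analyses use tumor response only as PR/CR versus SD/PD; adding a rank analysis of the percent change already measured would raise power for moderate-to-strong associations

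*Combined protocol and SAP*

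**What the plan says.** Section 3.3 states the exploratory aim: "To identify predictive biomarkers to pembrolizumab and lenvatinib which correlate with intracranial and extracranial responses". It also covers toxicity.

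Tissue markers are to be measured quantitatively on a 0 to 255 score (7.1.2.10.3). For their relation to outcome, the same section says "Associations between continuous AQUA scores and binarized outcome variables (such as response) will be done by ANOVA". It adds "Multivariable models will be generated to predict response" without saying what form the outcome takes. Survival endpoints are handled separately by Cox models and Kaplan-Meier curves.

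Section 8.3 says that baseline tissue markers "will be compared between non-responders (SD and PD) versus responders (PR and CR) using a mixed methods approach". For patients with on-treatment tissue it says "Differences in these markers by response will be assessed using two-sample t-test".

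The outcome behind these categories is continuous. Section 7.1.2.9.4 sums the largest diameters of up to five brain lesions, refers the sum to baseline, and calls a decrease of at least 30% a partial response. Section 7.1.2.9.7 puts the scans at weeks 6 and 12 and then every 12 weeks.

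**The concern.** The Simon rules need a yes/no response. The biomarker analysis does not, and no section gives a reason for carrying the cut over. After the cut, a 29% decrease is pooled with rapid progression and a 31% decrease with complete response. At the design response rates the responder group is small: 0.20 × 27 = 5.4 patients in melanoma and 0.30 × 29 = 8.7 in RCC. Tissue will come from fewer patients, because the fresh biopsy can be waived (2.1, 5.3). A tissue marker with a real, fairly strong relation to shrinkage could be missed although the same scans carry more information about it. The Cox models do not fill the gap, since they address survival.

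**Working it through.** **Inputs.** Target response rates of 20% (melanoma) and 30% (RCC), and 27 and 29 evaluable patients, all from 8.2. The documents give no power figure for the biomarker analyses, no marker-shrinkage correlation (rho) and no distribution of shrinkage.

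**The plan's own figures first.** The exact two-stage binomial calculation reproduces the designs that supply these rates.
- Melanoma (stop at 0/13, reject at 4 or more of 27): alpha 0.0416 at 5%, power 0.801 at 20%.
- RCC (stop at 2 or fewer of 18, reject at 7 or more of 29): alpha 0.0497 at 12%, power 0.801 at 30%. The RCC null is not labelled; 12% is assumed from the comparator rate in 8.2.

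**Information kept by the cut.** For a normal outcome cut at upper-tail share p, the efficiency relative to the uncut outcome is φ(z_p)² / [p(1−p)].
- p = 0.20: 0.2800² / 0.16 = 0.490.
- p = 0.30: 0.3477² / 0.21 = 0.576.
- At the null rates it is lower: 0.224 at 5% and 0.379 at 12%. The maximum, at 50%, is 0.637.
- With non-normal shrinkage (uniform, t with 5 df, lognormal skew either way) the loss ranges from 39% to 73% at p = 0.20 and from 37% to 64% at p = 0.30.

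**Against an analysis the trial could actually run.** Percent change does not rank patients who progress by new lesions, so some must share a worst rank. If a share t is tied, the efficiency of Spearman relative to the untied linear correlation is (3/π) × C² / [(1−t³)/12], with C = (t/2)φ(c) + [1−Φ(c√2)] / (2√π) and c = Φ⁻¹(t).
- t = 0.40: C = 0.258, efficiency about 0.81. The two-group analysis keeps 0.490/0.81 = 0.60 (melanoma) and 0.576/0.81 = 0.71 (RCC) of that, a loss of about 40% and 29%.
- t = 0.60: the loss is about 29% and 17%.

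**Simulated power.** One marker, two-sided 5%, bivariate normal marker and shrinkage, response defined as the top 20% or 30% of shrinkage, 20,000 replicates. Runs agree to about a point.

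| rho (assumed) | Melanoma n=27: two-group | Rank, 40% tied | RCC n=29: two-group | Rank, 40% tied |
|---|---|---|---|---|
| 0.2 | 10% | 14% | 12% | 15% |
| 0.4 | 29% | 46% | 37% | 50% |
| 0.5 | 44% | 67% | 55% | 70% |
| 0.6 | 60% | 86% | 74% | 89% |

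Other results at rho 0.5:
- With 60% tied, the rank analysis has about 60% (melanoma) and 63% (RCC).
- With no ties, the linear correlation has 78% and 81%.
- With tissue from only 20 patients per cohort and 40% tied: 32% versus 53% (melanoma) and 39% versus 52% (RCC).

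At rho = 0 every method rejects about 5% of the time.

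**The case against.** **Scope.** A reader might infer that all the biomarker work is affected, and with it the whole exploratory objective. The documents do not support that. The stated cut covers tissue markers. Section 8.3 gives the blood cytokine, flow cytometry and single-cell analyses as repeated-measures ANOVA with no response cut. The toxicity part of the objective and the Cox models are separate. Section 7.1.2.10.3 names response only as an example of a binarized outcome. This objection stands and limits the point.

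**Size.** A reader might also infer that half the usable information is thrown away. The 49% and 58% are measured against an untied linear correlation under normality, which the trial cannot fully realize. Against a tied-rank analysis the loss is smaller, and smaller still as the tied share rises. This also stands.

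**Multiplicity.** Section 7.1.2.10.3 lists about ten markers and leaves the list open. At 0.05/10 = 0.005 and rho 0.5, the rank analysis with 40% tied has only about 35% power with full tissue and a little over 20% with 20 samples. So the documents do not support saying that the trial's data would have shown a marker the planned test misses. The rank analysis improves the chance without making it good.

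**What percent change leaves out.** mRECIST response requires confirmation at 12 weeks (7.1.2.9.4), and best percent change does not. Locally treated lesions leave the sum (5.5.4). Measurable extracranial disease is not an entry requirement (5.1.1). Patients who miss the first scan, including deaths from extracranial disease, are unevaluable unless they had clear clinical CNS progression (2.2, 5.7, 8.2). These are reasons to add the rank analysis with stated rules and to keep the responder comparison.

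**Preference.** Responder versus non-responder does answer the objective as worded, the work is exploratory, and percent change could be analyzed later. A later analysis would not be prespecified, however, and prespecifying it now costs little.

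**Conclusion.** The point holds for tissue markers and tumor response. The plan's only stated form of that outcome is the two-group split, and the diameters already collected would support a more powerful analysis. At rho 0.5 the gain over the planned test is about 23 points in melanoma and 15 in RCC with 40% tied at worst rank (67 − 44 and 70 − 55). It is about 16 and 8 points with 60% tied (60 − 44 and 63 − 55). At rho 0.2 it is 3 to 4 points, and neither analysis would be likely to find the marker.

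These figures rest on a bivariate normal model, an assumed rho, an assumed tied share, one marker tested at 5%, and true response rates equal to the design targets. Lower response rates would make the cut costlier. The samples of 27 and 29 are upper limits for tissue. This is a worthwhile improvement to an exploratory analysis; the primary result and the go/no-go decision are unaffected.

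**What to change.** In 8.3 and 7.1.2.10.3, add a prespecified rank analysis (Spearman or rank regression), within each cohort, of the continuous tissue marker against best percent change from baseline in the sum of target diameters. Report it beside the responder comparison, which carries the confirmation requirement. State these conventions in advance:

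- Use intracranial change for intracranial response. Use extracranial change for extracranial response, only in patients with measurable extracranial disease.
- Give a shared worst rank to patients whose best response is PD by new lesions or clear clinical CNS progression, and to those counted as PD under the local-therapy rule in 5.5.4.
- For other patients with a locally treated lesion, compute change on the remaining untreated lesions against the baseline of those same lesions.
- Handle patients with no first scan as in the evaluability definition for the primary endpoint, with worst rank as a sensitivity analysis.

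The cost is SAP wording, a little more analysis work, and a worst-rank convention fixed before the data are seen. It needs no extra patients, scans or samples, and the primary endpoint and Simon rules do not change.
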